2.0 Objectives

2.1

The purpose of this study is to expand Adhere.ly (<https://adhere.ly/>)—a web-based platform to improve provider implementation and patient engagement in homework (i.e., between-session practice of skills learned during therapy) during mental health treatment—to include new features and therapeutic exercises for adult patients, develop a plan for its implementation and sustainment, and preliminarily evaluate it by conducting a feasibility Optimization, Effectiveness, and Implementation (OEI) Hybrid trial.

Aim 1. Understand and prioritize key stakeholder goals, challenges, affordances, and constraints

We will use an exploratory sequential (qual→quant) mixed-methods design to conduct semi-structured focus groups (qual) with mental health patients, providers, and administrators and a survey (quant) with providers. We will conduct 4 focus groups per stakeholder group (patient, provider, administrator) and each focus group session will include up to 6 participants. We will enroll 100 providers to complete the survey. Analyses will inform the design of new Adhere.ly features and exercises and an implementation/sustainment (I/S) blueprint.

Aim 2. Optimize, preliminarily evaluate, and implement Adhere.ly in community practice settings

We will conduct a small-scale feasibility OEI Hybrid trial with 30 community mental health providers randomized to Cognitive Behavioral Therapy (CBT) alone (n=25) vs. CBT+Adhere.ly (n=25), and 60 treatment seeking and provider-referred adult patients with clinically elevated anxiety and/or depression (outcomes), which we will assess at baseline and 3-months post-baseline. We will assess homework use by providers and adherence of patients (targets) weekly via session audio recordings and patient-report. We will optimize new Adhere.ly features and exercises, and our I/S blueprint during the trial and assess implementation outcomes post-implementation.

2.2

This is a feasibility trial and is not powered for hypothesis testing.

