3.0 Background

3.1

Homework is one of the most integral components of high-quality mental health treatment

Mental health disorders affect 1 in 6 youth and 1 in 5 adults in the U.S. and are associated with costly physical and behavioral health problems. The quality of services these patients receive *vs.* should receive is highly variable and characterized as a “quality chasm” by the IOM.¹ Homework, or between-session practice of skills learned during therapy, is one of the most integral, yet underutilized components of high-quality, evidence-based mental health treatments (EBTs) such as Cognitive Behavioral Therapy (CBT).^{2,3} Homework exercises are assigned by providers in-session and completed by patients between sessions with the goal of practicing therapeutic skills in the environment

where they will be needed most.⁴ Homework enables the generalization of skills and behaviors learned during therapy, facilitates treatment processes, provides continuity between sessions, allows providers to better grasp patients' learning, and strengthens that learning, leading to improved maintenance of treatment gains.⁴⁻⁶ Meta-analytic and systematic reviews have shown that homework use by providers and adherence by patients predict increased treatment engagement, decreased treatment dropout, and medium-to-large effects on improvement in clinical outcomes (Cohen's $d=.45\text{--}.77$).⁷⁻¹¹ Simply put, 68% vs. 32% of patients can be expected to improve when therapy involves homework.⁹

Innovative solutions are needed to address barriers to the implementation of homework

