Providers will be randomly assigned to administer either CBT alone (n=25) or CBT+Adhere.ly (n=25). All providers will be asked to administer CBT as they usually would for each patient, either in-person or via telemedicine, with CBT+Adhere.ly providers integrating Adhere.ly into treatment with their patients. To minimize risk of CBT alone (i.e., “control”) providers being less motivated to refer cases, providers will be informed of their assignment only after their first study-eligible patient has been enrolled. Each provider will be asked to treat 3 patients over the course of 3 months. Providers will be asked to audio record their treatment sessions using either audio recorders provided by the study team, or audiorecording software on their computer, if preferred. Clients will have the option to audio record the treatment sessions through their consent. Providers will be asked to upload those recordings to REDCap either weekly or bi-weekly. Providers will receive automated weekly emails with a reminder to upload audio recordings and a link to a REDCap form for uploading recordings. This form will ask the provider to enter their name, the name of the patient being treated, the session number, and whether the session was conducted in-person or over telemedicine. Providers who have not uploaded a recording after 2 weeks will receive a follow-up phone call from study staff to provide reminders and assistance where needed.

Assessment Strategy and Measures

Trial questionnaires are shown in Table 1. Baseline and 3-month post-baseline questionnaires will be completed by patients via REDCap surveys. Study staff will email or text patients a link to the survey through the REDCap system and will be available to

remotely assist patients in completing questionnaires. As stated previously, GAD-7 and PHQ-8 will be administered to screen potential participants for eligibility criteria and will be administered prior to obtaining informed consent. The informed consent document will specify that these data will be included with participants' study data if they are eligible and agree to participate or will not be included if they are ineligible or decide not to participate.

Table 1. Assessment Measures for Trial

Domain	Informant	Measure	Time Point	
			B	3M
Demographics	Provider	Provider Demographics Questionnaire	✓	
	Patient	Patient Demographics Questionnaire		
Attitudes Toward Homework	Provider	Attitudes Toward Homework Questionnaire (ATHQ) ¹²	✓	✓

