Anxiety Severity	Patient	General Anxiety Disorder-7 (GAD-7) ^{40,41}	✓	✓
Depression Severity	Patient	Patient Health Questionnaire-8 (PHQ-8) ⁴²	✓	✓
Quality of Life	Patient	Health-Related Quality of Life (CDC HRQOL-14) ⁴³	✓	✓
Therapeutic Alliance	Patient	Working Alliance Inventory- Short Revised (WAI-SR) ⁴⁴		✓
Treatment Satisfaction	Patient	Client Satisfaction Questionnaire (CSQ-8) ⁴⁵		✓

Note. B=Baseline; 3M=3-Month Follow-Up.

Provider homework use, patient homework adherence, and treatment fidelity

Patient homework adherence will be assessed weekly on the day of their next session using a REDCap survey, a link to which will be sent via automated text-message and/or email reminders, or via telephone by study staff after 1 day of no response. The first 4 items of the Homework Rating Scale II (HRS II) will be used to measure patient homework adherence.⁴⁶ Session audio recordings will be observationally coded by independent coders blinded to study aims. Provider adherence and competence in reviewing, designing, and assigning homework (i.e., homework use) will be assessed using the Homework Adherence and Competence Scale (HAACS).⁴⁷ Provider general therapeutic and CBT-specific skills to appropriately deliver CBT will be assessed by the Assessment of Core CBT Skills (ACCS).⁴⁸

Optimization

We will iteratively optimize Adhere.ly and our implementation strategies during the feasibility trial based on user data, error reports, support requests, and data from routine feedback interviews conducted by Adhere.ly, LLC. We will address unanticipated problems and opportunities encountered during implementation, remove unnecessary components and I/S strategies, and improve processes and functionality. We will develop a clear set of procedures for optimization and keep a log of all changes made for reporting purposes, consistent with the Trials of Intervention Principles outlined by Mohr and colleagues.⁴⁹

Implementation

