8.0 Study Timelines

8.1

Aim 1. Adult mental health patients, providers, and administrators will participate in one ≤90-minute focus group. Providers will be invited to complete a ≤15-minute survey.

Aim 2. Providers will participate in one \leq 60-minute consent and training process and twelve \sim 60-minute therapy sessions per study case. Study referral procedures will take an additional 5 minutes per patient. An additional 5 minutes per patient, per session will be required to upload audio recordings. Providers who participate in post-implementation interviews will spend an additional 45 minutes in the study. In all, the total amount of time spent in the study will be approximately 28 hours over the course of 9 months, only 4 hours of which will be spent engaging in study procedures beyond their everyday practice.

Patients will participate in a \leq 60-minute eligibility screening, consent, and baseline assessment process. Patients will participate in twelve \leq 60-minute therapy sessions, engage in twelve \sim 10-minute homework assignments, and spend \leq 5 minutes each week completing homework assessments. 3-month follow-up assessments will take \leq 30 minutes. Patients who participate in post-implementation interviews will spend an additional 30 minutes in the study. In all, the total amount of time spent in the study will be approximately 17 hours over the course of 6 months, only about 5 hours of which will be spent engaging in study procedures beyond the time they would have otherwise been receiving therapy from their provider.

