16.0 Data Management and Confidentiality

16.1

Aim 1 Data Analysis

Focus group transcripts will be coded by trained study staff in NVivo using a hybrid inductive-deductive, consensus-based content analysis,⁵²⁻⁵⁴ and the mCFIR tool.^{36,37,55} Coders will meet regularly to ensure consistency with code definitions and resolve inconsistencies via discussion to achieve consensus. Data aggregation queries will be used to create case memos and assign ratings for mCFIR constructs. Survey data will be analyzed to describe provider goals, challenges, affordances, and constraints. We will use the Expert Recommendations for Implementing Change (ERIC) matching tool to generate a list of potential implementation strategies for refinement.^{56,57} We will synthesize qualitative and quantitative findings to prioritize new features, exercises, and I/S strategies.

Aim 2 Data Analysis

Feasibility

We will assess feasibility of the proposed trial methodology using the following benchmarks, which were informed by the sample size needed for hypothesis testing in Phase II and expert recommendations.⁵⁸⁻⁶¹

Benchmarks: 50 providers will be enrolled in months 1-2 [20/month]); 60 patients will be enrolled in months 2-6 [8/month]); 70% of providers and patients will use Adhere.ly; 70% of session recordings will be uploaded; 70% of weekly HRS II assessments will be completed; 70% of patients will be retained at 3-month follow-up.

Evaluation

The small sample size prevents any conclusions about effectiveness; however, ANCOVA will be used to preliminarily assess-between group differences in clinical outcomes while co-varying for pre-treatment scores. ANOVA will be used to compare homework use and adherence. We also will preliminarily examine relations among study variables (therapeutic alliance, satisfaction).

Implementation

Interview transcripts will be coded by trained study staff in NVivo using the mCFIR

coding scheme developed during Aim 1. Data aggregation queries will be used to create case memos and assign ratings for mCFIR constructs, which we will examine between pre- and post-implementation using a modified CFIR matrix template. We will further synthesize qualitative with quantitative (i.e., mCFIR, RE-AIM) results to confirm and/or explain summative evaluation findings.

Table 2. RE-AIM outcomes

Dimension	Results

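### Section 16.1 compares weekly homework use and adherence by ANOVA without saying how repeated ratings or missing weeks are handled; either usual reading loses the time course or patients

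*Combined protocol and SAP*

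**What the plan says.** Section 2.1 (Aim 2) names the two outcomes and their frequency: "We will assess homework use by providers and adherence of patients (targets) weekly via session audio recordings and patient-report". Section 5.2 gives the instruments. Patient adherence uses the first four HRS II items: "Patient homework adherence will be assessed weekly on the day of their next session using a REDCap survey". Provider homework use is coded from session recordings with the HAACS. Section 8.1 sets the length: "Patients will participate in twelve" therapy sessions.

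The time index for recordings is already collected. The upload form in Section 5.2 asks for "the session number, and whether the session was conducted in-person or over telemedicine".

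The whole analysis of these data, in Section 16.1 under Evaluation, is the sentence "ANOVA will be used to compare homework use and adherence". It names no factors, summary score, session term or rule for missing weeks. The feasibility benchmarks in the same section include "70% of weekly HRS II assessments will be completed; 70% of patients will be retained at 3-month follow-up", and the upload of recordings also has a 70% benchmark.

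**The concern.** ANOVA applied to about twelve ratings per patient can mean two quite different things, and each has a cost.

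- **ANOVA on patient means.** Each patient's ratings are collapsed to one number, so the course over sessions is lost. Patients who leave early contribute only their first weeks, while those who stay contribute the full course. Section 9.3 removes patients who stop or interrupt CBT, and Section 13.1 removes the patients of a provider who withdraws. Section 3.1 reports that homework use and adherence "predict increased treatment engagement, decreased treatment dropout", so unequal follow-up between arms is at least plausible on the plan's own reasoning.
- **Repeated-measures ANOVA with listwise deletion.** This normally carries a session factor and an arm-by-session test, so it can show a time course. It uses only patients with no missing week, however, and the plan's benchmark allows 30% of surveys to be missing.

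The two problems are alternatives and do not add up. At stake is whether data already being collected can show when during treatment homework use and adherence differ between arms, and in how many patients.

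**Working it through.** **Inputs from the documents.** 60 patients (11.1); 12 sessions (8.1); 70% benchmarks for HRS II surveys, recordings and retention (16.1). HRS II is asked on the day of the next session, so there are 11 or 12 ratings per patient. With 12, there are 60 × 12 = 720 planned patient-weeks. The plan gives no power, effect size, SD or pattern of missing weeks for these outcomes, so there is no figure of its own to reproduce. The profiles, correlations, decline and dropout rates below are assumptions.

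**1. Patient means: fading versus constant effect.** Let the arm difference in week w be max(0, 1 − (w − 1)/7) for w = 1 to 11. The sum is (7 + 6 + 5 + 4 + 3 + 2 + 1)/7 = 4, so the mean is 4/11 = 0.364. A constant difference of 0.364 has the same mean. Yet the fading effect averages 0.857 in weeks 1–3 and 0 in weeks 9–11. A linear fade from 1 to 0 over 12 weeks behaves alike: its mean is 0.50, with 0.86 in weeks 1–4 and 0.14 in weeks 9–12. A constant 0.50 has the same mean.

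**2. Patient means: different weeks.** Let adherence fall linearly by D over 12 weeks in both arms, with no true effect. An arm seen only in weeks 1–8 has fallen on average by 3.5/11 = 0.318 D. An arm whose misses are spread evenly has fallen by 0.500 D. The spurious difference is 0.182 D, in favour of the arm seen early. This is an extreme case, because every patient in one arm stops at week 8.

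A less extreme simulation used 200 runs per setting, 30 patients per arm, 70% weekly completion, a fall of 0.05 to 0.15 points per week, dropout of 40% vs 20% or 45% vs 15%, patient SD 0.7 and weekly SD 0.8. The patient-mean ANOVA had a bias of −0.02 to −0.11 points against Adhere.ly, with an SE of 0.20–0.23. A mixed model with a week term had a bias within about ±0.02 (Monte Carlo error 0.015) and an SE of 0.20–0.22.

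**3. Repeated-measures ANOVA with listwise deletion.** With independent misses, the share of complete patients is p^K. With misses correlated within patients (beta-binomial, correlation ρ), it is B(a + K, b)/B(a, b), where a = 0.7(1/ρ − 1) and b = 0.3(1/ρ − 1). At 70% average completion, and K = 12 unless stated:

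| Pattern of misses | Complete of 60 | Dropped |
|---|---|---|
| Independent: 0.70^12 = 0.0138 | 0.8 | 59.2 |
| Independent, K = 11: 0.70^11 = 0.0198 | 1.2 | 58.8 |
| ρ = 0.1 | 4.1 | 55.9 |
| Linear dropout to 70% plus scattered misses: 0.70 × (0.70/0.85)^12 = 0.068 | 4.1 | 55.9 |
| ρ = 0.2 | 8.4 | 51.6 |
| ρ = 0.3 | 12.9 | 47.1 |
| ρ = 0.5 | 21.7 | 38.3 |
| Dropout only, constant hazard 0.0677: 0.9323^11 = 0.462 | 27.7 | 32.3 |
| All or none (ρ = 1) | 42.0 | 18.0 |

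In the last row the 18 lost patients have no ratings at all, so no method would keep them. If completion beats the benchmark and misses are independent, about 4 of 60 patients are complete at 80%, 17 at 90% and 32 at 95%.

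**4. All available ratings.** At the benchmark a mixed model uses 0.70 × 720 = 504 patient-weeks under any of these patterns with K = 12. Listwise deletion uses 0.83 × 12 ≈ 10 patient-weeks in the independent case, and the full 42 × 12 = 504 in the all-or-none case.

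**The case against.** The strongest reply is that this is a feasibility trial. Section 2.2 disclaims power for hypothesis tests, and Section 16.1 says the sample is too small for conclusions on effectiveness. A comparison of patient means is a recognised summary-measure analysis, and Table 2 already lists degree of use and adherence, survey completion and attrition. This limits the importance of the point. It does not remove it, because Table 2 plans none of these by week, and an estimate that uses all ratings serves a feasibility trial at least as well.

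Four stronger readings are tempting, and the documents do not support them.

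- *The plan excludes a session term.* It is silent. The sentence could cover a repeated-measures ANOVA, which would contain one.
- *A repeated-measures ANOVA would lose nearly every patient.* That needs nearly independent misses at about 70% completion. The documents give no pattern of misses, 70% is a benchmark and not a forecast, and Section 5.2 has staff telephone after one day without a response.
- *The comparison of means is badly biased.* The largest simulated bias is about half an SE, the smallest is near the Monte Carlo error, and every driver is assumed. Applying 70% completion on top of that dropout leaves fewer ratings than the benchmark. The mixed model is hardly more precise.
- *The sustainment aim is defeated.* In Sections 2.1 and 5.1, sustainment belongs to the implementation blueprint for practice settings, not to the persistence of an effect within a patient.

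**Conclusion.** The point holds as a conditional one, and the change should be made. Section 16.1 does not define the analysis of the trial's two named targets, and neither usual reading suits weekly data with missing weeks.

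Under patient means, the inability to tell a fading effect from a constant one is arithmetic and needs no assumption about SD or dropout. The misalignment of weeks is real in principle, but probably small. Under listwise deletion the loss runs from many patients to nearly all: about 18 to 59 of 60 at 70% completion. It exceeds 45 of 60 for within-patient correlations of misses up to 0.3, and falls to about 32 under pure dropout. The lower end reflects patients with no data, not a fault of the method.

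The gain from a better model is a visible time course and the use of every rating, more than a smaller standard error. The figures rest on 12 ratings per patient, completion at the benchmark, and assumed patterns of misses and effect over time.

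**What to change.** In Section 16.1 (Evaluation), replace the ANOVA sentence with text to this effect:

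> Weekly HRS II and per-session HAACS scores will each be analysed with a likelihood-based linear mixed model using all available ratings. Fixed effects will be arm, session number (survey week for HRS II) and arm by session; random effects will be provider, as the randomised unit, and patient. The arm difference will be estimated with equal weight over the planned sessions, and descriptively for sessions 1–4 and 9–12, with 95% confidence intervals. Missing ratings will be reported by week and arm.

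The first and last third are an example; any early and late windows will do if they are fixed in advance. The session number is on the recording upload form. For HRS II the week must be taken from the survey timing.

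The cost is a little more analysis work and no new data. Late-session estimates will be imprecise and should be labelled descriptive. With 60 patients and 50 providers (60/50 = 1.2 each on average), provider and patient variances may be hard to separate, so the plan should say what is done if the model does not converge. The model assumes that missingness depends only on observed data. If patients who skip homework also skip the survey, it does not cure that, which is a further reason to report missingness by week and arm.

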5.0 Procedures Involved

5.1

Aim 1. Understand and prioritize key stakeholder goals, challenges, affordances, and constraints

Aim 1 of this study will use an exploratory sequential (qual→quant) mixed-methods design to conduct semi-structured focus groups (qual) with mental health patients, providers, and administrators and a survey (quant) with providers. We will conduct 4 focus groups per stakeholder group (patient, provider, administrator) and each focus group session will include up to 6 participants. Half of the focus groups will consist of stakeholders from public healthcare institutions and the other half will consist of stakeholders from private healthcare institutions. We then will enroll 100 providers to complete the survey. Analyses will inform the design of new Adhere.ly features and exercises and an implementation/sustainment (I/S) blueprint.

Aim 2. Optimize, preliminarily evaluate, and implement Adhere.ly in community practice settings

Aim 2 of this study will use a randomized controlled OEI Hybrid trial design. The trial will include 50 community mental health providers randomized within their respective practice locations to administer CBT+Adhere.ly (n=25) vs. CBT alone (n=25) to a total of 60 treatment-seeking adult mental health patients with clinically elevated anxiety and/or depression-referred and treated by providers. Study staff will conduct pre- and post- implementation assessments remotely with providers and will facilitate web-based administration of baseline and 3-month post-baseline assessments with patients via REDCap. Treatment sessions may be audio recorded and uploaded to REDCap by providers and coded by study staff to assess provider assignment and assessment of homework. Clients will have the option to allow providers to audio-record their therapy sessions through the consent. Patient homework adherence will be assessed weekly the day of their next session using a REDCap survey, a link to which will be sent via automated text-message and/or email reminders, or by telephone after 1 day of no response.

5.2

 Audio/Video Recording	 Psychophysiological Recording
 Behavioral Interventions	 Record Review - Educational
 Behavioral Observations and Experimentations	 Record Review - Employee

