Pre-implementation assessments will take place during Aim 1. Study staff will conduct remote, \leq 45-minute individual post-implementation interviews with \leq 10 patients and \leq 10 providers who participate in the CBT+Adhere.ly condition. Participants will be recruited via telephone by study staff and scheduled for an interview. Informed consent from providers and patients to participate in these interviews will have been obtained by study staff during the initial consent process for the trial. These interviews will use the mCFIR tool to assess perceptions about Adhere.ly's implementation and performance within each

of the mCFIR domains. To complement this evaluation of implementation processes, we will evaluate implementation outcomes with respect to Reach, Effectiveness, Adoption, Implementation, and Maintenance guided by the RE-AIM framework.^{50,51} These data will be added to the robust mCFIR data to contribute to an overall summative evaluation.

5.3

The standard of care procedures for adults with clinically elevated anxiety and/or depression is traditional CBT from provider.

5.4

There are no additional foreseeable risks to the above procedures in need of further mitigation beyond those ordinarily incurred in working with this population. Standard operational procedures of clinics specify responsibilities for handling dangers to self and others and safety planning in the event of domestic violence.

5.5

N/A

5.6

N/A

5.7

N/A

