Reach	Number of potential providers and patients available for recruitment; percentage eligible/ineligible, invited, and enrolled; sample characteristics; reasons for ineligibility and varying levels of engagement; ambiguities regarding eligibility criteria
Effectiveness	Attrition and related patient characteristics; adverse events; satisfaction; impact
Adoption	Estimated number of settings for future trials; settings and stakeholder characteristics
Implementation	Percentage of providers and patients who use Adhere.ly; average number of exercises used by providers and patients; percentage of session recordings uploaded; percentage of weekly HRS II completed; degree of use and adherence; provider/patient time costs; patient retention; assessment time burden; completed assessments; missing items; broken/lost/stolen equipment; technical issues
Maintenance	Clinical outcomes at 3-months post-baseline

16.2

All data collected during the trial will be securely stored in a REDCap database, including informed consent/assent documents, questionnaire data, and audio recordings. Data obtained from Adhere.ly platform for the purposes of this study will include names, phone numbers, and email addresses, and usage data relating to providers practicing, assigning, and assessing exercises, and patients completing those exercises. These data will be downloaded from Adhere.ly and merged with the data in REDcap. Only IRB-approved and trained study personnel will have access to the REDCap project and access will be limited to information and modules that are required for them to complete their assigned study-related tasks. All identifiers will be marked as such in REDCap and will not be included in the final exported dataset, which will instead include assigned ID numbers.

We will use the following security measures to protect data sources:

1. all research data exported from REDCap will include ID numbers only
2. the codes that link the name of the participant and the study ID will be kept confidential in REDCap
3. computers and servers containing data will be password-protected to prohibit unauthorized access
4. online survey data collection will be accessible only by IRB approved study staff with secure logins
5. Adhere.ly includes state-of-the-art technical infrastructure—including encryption and other software, security practices, and business operational practices to ensure compliance with all major governing legislation, including HIPAA

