17.0 Provisions to Monitor the Data to Ensure the Safety of Subjects

17.1

N/A

17.2

N/A

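### Adverse events are a listed outcome, but the protocol describes no way of collecting them, so counts are likely incomplete and possibly unbalanced between arms

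*Combined protocol and SAP*

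**What the plan says.** The Effectiveness row of Table 2 (section 16.1) reads "Attrition and related patient characteristics; adverse events; satisfaction; impact". Adverse events are mentioned nowhere else. No definition, time window, source or method of summary is given.

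The data sources described are these:

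- **Questionnaires (section 5.2).** "Trial questionnaires are shown in Table 1": demographics, ATHQ, GAD-7, PHQ-8, HRQOL-14, WAI-SR and CSQ-8. None is an adverse-event form.
- **Weekly survey (section 5.2).** "Patient homework adherence will be assessed weekly on the day of their next session using a REDCap survey", with a staff call after one day of silence. Its content is the first four HRS II items.
- **Session recordings.** Under section 5.1 they are "coded by study staff to assess provider assignment and assessment of homework"; section 5.2 adds rating of CBT skill. They are not complete: "Clients will have the option to allow providers to audio-record their therapy sessions through the consent".
- **Safety monitoring.** Section 17.0, "Provisions to Monitor the Data to Ensure the Safety of Subjects", has N/A under both 17.1 and 17.2.

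Two further kinds of contact lie outside the shared schedule. Post-implementation interviews (section 5.2) are held with at most 10 patients and at most 10 "providers who participate in the CBT+Adhere.ly condition"; the consent wording in section 21.2 ties them to that condition too. Optimization (section 5.2) uses platform usage data, error reports, support requests and "data from routine feedback interviews conducted by Adhere.ly, LLC". No arm is named for these, but they concern the platform.

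**The concern.** An outcome with no described collection rests on whatever patients or providers happen to volunteer. Events that were never asked about cannot be recovered at the analysis stage.

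Two misreadings could follow. A count at or near zero could be reported as an absence of harm, when it may show only that nobody asked. A higher count under CBT+Adhere.ly could be taken as a feature of the platform, when it may show only that more people in that arm were interviewed.

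The patients have clinically elevated anxiety and/or depression, so worsening is a relevant harm, and the scores needed to describe it are already planned. The feasibility benchmarks in section 16.1 look ahead to Phase II. Whether harms can be recorded equally in both arms is one of the things this trial could usefully establish.

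**Working it through.** The plan states no adverse-event rate or expected count, so there is no figure to reproduce. The check is a comparison of sources, followed by an illustration.

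**Step 1: which contacts exist, in which arm, and do they ask about harms?**

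| Contact | Arms | Described as asking about harms? |
|---|---|---|
| Weekly survey, four HRS II items (5.2) | Both | No |
| Telephone back-up to the weekly survey (5.2) | Both | No |
| Baseline and 3-month questionnaires, with staff help (5.2) | Both | No; GAD-7 and PHQ-8 can show worsening |
| Session recordings (5.1, 5.2) | Both, optional | No; coded for homework and CBT skill |
| Post-implementation interviews (5.2) | CBT+Adhere.ly only | No; mCFIR tool |
| Feedback interviews and support requests (5.2) | Not named; probably Adhere.ly users | No |

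No source asks, and the extra contact falls mainly or wholly on one arm.

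**Step 2: how unbalanced could the counts be?** Assumptions, none from the documents:

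- n = 30 patients per arm (the plan gives 60 in total; providers are randomized and no patient split is stated);
- the same true rate p in both arms;
- a share s of events surfaces unasked in either arm;
- m = 10 Adhere.ly patients are interviewed, the plan's maximum, and all disclose fully.

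Expected counts:

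- control = n·p·s
- Adhere.ly = n·p·s + m·p·(1 − s)
- ratio = 1 + (m/n)·(1 − s)/s = 1 + (1 − s)/(3s), so p cancels

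| s | Ratio |
|---|---|
| 0.2 | 1 + 0.8/0.6 = 2.33 |
| 0.3 | 1 + 0.7/0.9 = 1.78 |
| 0.5 | 1 + 0.5/1.5 = 1.33 |
| 0.7 | 1 + 0.3/2.1 = 1.14 |

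In counts, with p = 20% and s = 0.5, 30 × 0.20 = 6 events occur per arm. Control records 6 × 0.5 = 3.0, and Adhere.ly records 3.0 + 10 × 0.20 × 0.5 = 4.0. Both are short of 6, and they differ although the true rates are equal. If the interviews bring out no events, the second term vanishes and the ratio is 1.0; the counts are then incomplete but balanced.

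**Step 3: what would existing contacts cover if they asked?** Taking one weekly survey for each of the twelve sessions in section 8.1, the maximum is 60 × 12 = 720 surveys. At the 70% completion benchmark, 0.7 × 720 = 504 are returned. At the 70% retention benchmark, 0.7 × 60 = 42 patients have a 3-month score and 18 do not.

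**Step 4: does adding the item remove the imbalance?** If only the shared item is counted, the expected ratio under equal true rates is 1.0. If interview reports are pooled into the same count, the Step 2 formula applies again. With the item capturing 70% of events, the ratio is 1.14. With 49% (0.7 sensitivity × 0.7 completion), it is 1 + 0.51/(3 × 0.49) = 1.35. The two kinds of report therefore need to be kept apart.

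**The case against.** The strongest reply is that this is a small feasibility trial, described as minimal risk in section 14.1. No between-arm safety test is planned, and Table 2 is a summary framework. Clinics have their own procedures for danger to self or others (section 5.4). Both arms have staff calls and help with questionnaires, and section 16.3 requires every participant contact to be documented. That section also mentions SOPs and a Manual of Procedures, which are not in the file and may contain an adverse-event form.

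Much of this stands, and it limits what can be said. Three stronger readings do not hold:

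- A reader might infer that the study collects no adverse events at all. The documents show only that the protocol describes no collection.
- A reader might infer that the counts will be lopsided. The interviews are capped and follow an implementation tool, and the arm for the feedback and support contacts is an inference. Imbalance is a possibility, not a demonstrated result.
- A reader might want to attach an exact upper confidence limit to a zero count. That limit presumes every patient was fully ascertained, which is what is missing here.

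The central gap remains. The contact log and clinic procedures are passive, and no route from the clinics to the study record is stated. The lack of a planned test does not make an uncollected outcome reportable.

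**Conclusion.** The point holds as a gap in described collection. Adverse events are promised as a result, no described procedure gathers them, and the contact known to exceed the shared schedule is confined to CBT+Adhere.ly. Reported counts are likely incomplete and possibly unbalanced.

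The extent of under-counting cannot be derived from the documents. The count ratio of about 1.1 to 2.3 rests on 30 patients per arm, equal true rates, 10 interviewed patients who disclose fully, and 70% down to 20% of events surfacing unasked. With less disclosure the ratio moves toward 1.0. No safety conclusion in either direction could rest on such counts.

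**What to change.** 1. Define adverse events and state the observation window. Section 1.1 gives patient participation as 3 months and section 8.1 as 6 months; these need to be reconciled.
2. Add one identical adverse-event item to the weekly and 3-month REDCap surveys in both arms, including the telephone back-up.
3. Ask it once more, by the same link or call, when a patient stops or is withdrawn. Sections 9.3 and 13.1 end participation when CBT stops or the provider withdraws, and no exit contact is described, so a 3-month item alone would miss these patients. Report reasons for leaving by arm.
4. Report by arm the number whose GAD-7 or PHQ-8 worsened from baseline by an amount fixed before analysis, beside the number with no 3-month score. This needs no new data, but it measures deterioration and does not cover every harm.
5. List events learned only through interviews, feedback or support contacts separately, outside the between-arm count.
6. Present all of this descriptively, with the number of patients asked as the denominator. The revision history shows providers already enrolled at this version, so the item may cover only part of the sample; the score table can use every patient with both assessments.

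The cost is a brief item per survey, a short exit contact, one table and a protocol modification. If collection is not wanted, adverse events should come out of Table 2.
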